5.10 REPLACING FULL COLLECTION BAG

- a. Do not turn off the AirPurge. Open a new Cartridge package and remove Collection Bag by disconnecting Luer connector.
- b. Ensure AirPurge is **not** purging (PURGING Indicator **not** lit) and pause flow into the AirPurge (*e.g. clamp line*).
- c. Disconnect Luer connector to remove Full Collection Bag and attach New Collection Bag.
- d. Resume flow.

5.11 REPLACING EMPTY I.V. BAG

- a. Do not turn off the AirPurge. Replace I.V. bag as usual. (*The AirPurge will remove air admitted into primary I.V. line and divert liquid flow back to study subject line*).
- b. If drip rate is too slow, increase the drip rate until “PURGING Light is off and flow is resumed to the study subject.

5.12 FLUID WARMERS

- a. Any Fluid Warmer can be used based on the Clinical Site’s preference and routine standard of care practices.
- b. Follow Fluid Warmer manufacturer Instructions for Use (IFU).
- c. Install Fluid Warmer **ABOVE** the AirPurge System. The AirPurge System can be connected to the Fluid Warmer with standard extension I.V. line sets.

5.13 INFUSION PUMPS

Infusion Pumps should *not* be used on the AirPurge line.

5.14 INDICATORS AND ALARMS

Refer to page 13 of the AirPurge Operator’s Manual for further information on Indicators and Alarms. The incidence and timing of any Indicator Light or Alarm will be documented on the Operative Report.

Indicator	Alarm	Solution
TEMP	Yes	Discontinue Use. Turn Device Off and Open Door. Monitor Air Bubbles Manually & Contact ASP for Service.

Anesthesia Safety Products - Confidential Information

This document and the subject matter contained herein is the property of Anesthesia Safety Products and may not be copied, reproduced, or disclosed to others without the expressed written permission of a duly authorized agent of the company.

TURN OFF- OPEN DOOR	Yes	Discontinue Use. Turn Device Off and Open Door. Monitor Air Bubbles Manually & Contact ASP for Service.
DOOR	Yes	Ensure Cartridge is Inserted Correctly, Red Retaining Clip Removed & Door Securely Latched. If Alarm Persists Discontinue Use and Contact ASP for Service.
↑↑VERT	Yes	Reposition Device on I.V. Pole using Clamp. When Positioned Correctly Device Resets Itself.
PURGING	PURGING Indicator Lights when device Purging. After 1 minute (Indicator begins Blinking + Alarm)	DO NOT TURN OFF Device. Check I.V. Line for Obstructions or I.V. bag Empty* Very Low Flow Rates can Cause Purge Times > 1 Minute; Wait for Alarm to Silence.

*If Alarm persists discontinue use. Turn device off and open door. Monitor air bubbles manually and contact ASP for service.

5.15 AIRPURGE SYSTEM DISPOSABLE CARTRIDGE STORAGE

Temperature	-20 to 60°C
Relative Humidity	10 to 93 %RH
Air Pressure	500 to 1060hPa (15-31Hg)
Elevation	0 to 9800 feet

5.16 CLEANING AND MAINTENANCE

- a. Cartridges and Collection Bags are *for single use only*. Dispose in your medical waste.
- b. Refer to Operator’s Manual for AirPurge Device cleaning and disinfecting instructions.

5.17 DEVICE RETURNS

Any AirPurge Devices or Cartridges that do *not* function properly should be returned to the Study Sponsor for device complaint evaluation after Study Sponsor notification. Contact Customer Service for return instructions.

6.0 STUDY PROCEDURE

6.1 SCHEDULE OF EVENTS

Data collection for this post-approval study will occur as described in the below table. Data collection and required study visits are limited to the preoperative completion of the CS001-12LL Eligibility Checklist / Demographics and the Operative Day which involves both data collection from Clinical Site Personnel on the CS001-13LL Operative Report and objective measurements collected via the Data Monitor which is attached to the USB port on the AirPurge System. Refer to Schedule of Events provided in **Attachment 1** for additional details.

Data Collection	Visit Timeframe
CS001-12 Eligibility Checklist / Demographics	Prior to Procedure* (Visit 1)
CS001-13 Operative Report	Operative Day (Visit 2)
Data Monitor	Operative Day (Visit 2) (Collected by Sponsor upon completion of Clinical Site's enrollment/ procedures**)

*If study-specific Informed Consent Document (ICD) used, ICD must be signed *prior to* completion of CS001-12 Eligibility Checklist / Demographics

** Collection may occur at periodic intervals during study to verify Data Monitor operation

6.2 ELIGIBILITY CHECKLIST / DEMOGRAPHICS

Visit 1 will involve Clinical Site personnel collection of the following data fields:

Subject ID
Date / Time
Age
Gender
Race
Height
Weight
Surface Area
Scheduled Procedure Reason / Diagnosis for Procedure
Medication History

6.3 OPERATIVE REPORT

Visit 2 will involve Clinical Site personnel collection of the following data fields:

Subject ID #
Procedure Date
Procedure Start and End Time
AirPurge Start Time and End Time
Procedure (circle one): arterial septal defect closure, ballooning of coarctation, craniotomy, craniosynostosis, patent ductus arteriosus, (pda) closure, pulmonary artery stent deployment, pulmonary valve balloon dilatation, spinal fusion, scoliosis or cardiac surgery involving cardiopulmonary bypass
Procedure Complications
Use of Fluid Warmer
I.V. Fluid and Bag Volume
Additional I.V. Line Activity
Confirm AirPurge used on Free-flow maintenance line
AirPurge Waste Collection Bag
AirPurge Alarms
AirPurge Complaints

Anesthesia Safety Products - Confidential Information

This document and the subject matter contained herein is the property of Anesthesia Safety Products and may not be copied, reproduced, or disclosed to others without the expressed written permission of a duly authorized agent of the company.

6.4 DATA MONITOR

Visit 2 will also involve the collection of the following objective measurements through the Data Monitor software:

- Total time (in milliseconds) that the AirPurge sensor detects incoming air in order to calculate total actual air volume captured
- How often purge mechanisms kicks in
- Frequency & Duration of Purging
- Total Time AirPurge device powered on, number of times device power turned on and off and number of Device Alarms Detected

7.0 STATISTICAL PLAN

This multi-center post-approval clinical study is *not* a comparative study design *nor* is the clinical design intended to support the functional safety and efficacy of the AirPurge System for the purposes of obtaining FDA approval. Therefore, there are *no* prospective safety / efficacy success criteria or endpoints. The overall goal of this post-approval study is information gathering in regards to the clinical value of the AirPurge System utilizing a set of controlled I.V. set-up parameters and group of procedures.

All available data will be entered into standard Excel spreadsheets for analysis purposes and data entry verified *prior to* the final analysis. Planned data analyses include:

- 1) **CS001-12LL Eligibility Checklist / Demographics:** Data will be analyzed using standard demographic variable presentation for age, race, gender, height, weight and surface area and to record any pre-existing conditions (medical / drug) that could impact intravenous fluid delivery during the procedure.
- 2) **CS001-13LL Operative Report:** Data collected will be used to evaluate the clinical activity in the clinical setting to provide key background regarding the overall procedure, I.V. fluid delivery parameters and the operation of the AirPurge. Data will be presented for individual study subjects, as applicable and for the overall study population as a whole.
- 3) **Data Monitor:** The Study Sponsor will analyze the objective measurement data collected from the Data Monitor software and correlate Data Monitor measurements with the clinical data collected from Clinical Site personnel and documented on the CS001-13LL Operative Report. Analytical measurements will include:
 - Total volume of air captured (mean, range and SD) for individual study subjects and the overall study population as a whole)
 - Duration of AirPurge purge mechanism activity (mean, range and SD) for individual study subjects and the overall study population as a whole)
 - Frequency of AirPurge purge mechanism activity (mean, range and SD) for individual study subjects and the overall study population as a whole) to answer questions concerning the necessity of purging over the duration of a procedure (e.g. number of purging episodes; length of time between purging episodes)

Anesthesia Safety Products - Confidential Information

This document and the subject matter contained herein is the property of Anesthesia Safety Products and may not be copied, reproduced, or disclosed to others without the expressed written permission of a duly authorized agent of the company.

-Summary of the incidence of AirPurge alarms and indicators will be prepared

-An analysis between the objective measurements collected with the Data Monitor and the clinical activity reported on the Operative Report to correlate what was occurring clinically during purging activity.

The final data analysis will be presented in text, tables, and graphical representations including a graphical time analysis of AirPurge usage over the duration of the procedure.

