2.0 STUDY OBJECTIVES

2.1 PRIMARY STUDY OBJECTIVES

The primary objectives of this post-approval clinical study are:

- 1) to measure the *amount of air removed from the intravenous (I.V.) line by the AirPurge System* in a clinical setting with standardization of the surgical procedure, I.V. fluid and flow rate
- 2) to measure the *frequency and duration of the AirPurge purging mechanism activity* in a clinical setting with standardization of the procedure, I.V. fluid and I.V. line.

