3.0 STUDY DESIGN

3.1 GENERAL DESIGN

The AirPurge Air Detection and Removal System Post-Approval Multi-Center Clinical Study is a prospective, observational, single arm / non-randomized post-approval study design. This multi-center post-approval clinical study is *not* a comparative study design *nor* is the clinical design intended to support the functional safety and efficacy of the *commercially available* AirPurge System for the purposes of obtaining FDA approval. Therefore, there is *no* investigational device and *no* prospective safety / efficacy success criteria or endpoints. The AirPurge System will be utilized for the current FDA approved intended use / indications for use. The overall goal of this post-approval study is information gathering in regards to the clinical value of the AirPurge System within the operating room setting utilizing a set of controlled I.V. set-up parameters including I.V. fluid, I.V. line including the usage of key I.V. pole accessory equipment and a standardized group of procedures.

The study endpoint is the discontinuation of AirPurge System usage during the procedure and therefore there are *no* post-procedure follow-up requirements minimizing the risk of lost-to follow-up study subjects. Study subjects will be recruited from the Clinical Sites' current patient population scheduled to undergo one of the inclusion criteria procedures. Subjects will be enrolled into the study in a sequential manner.

Data collection is limited to two time points:

The hard copy CS001-12LL Eligibility Checklist / Demographics case report form (CRF) will be completed *prior to* surgery. Operative Day data will be collected utilizing two data collection methodologies as follows:

- 1) CS001-13LL Operative Report: This hard copy case report form (CRF) will be completed by Clinical Site personnel and collect information on device performance from the clinician's perspective, intravenous line fluid delivery specifics, and relevant background concerning the procedure.

Anesthesia Safety Products - Confidential Information

This document and the subject matter contained herein is the property of Anesthesia Safety Products and may not be copied, reproduced, or disclosed to others without the expressed written permission of a duly authorized agent of the company.

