5.9 SYSTEM START-UP / CLEARING THE LINES

CAUTION: Only use I.V. lines with Luer Lock connectors. When connecting the I.V. line to the top and bottom of Cartridge, do **not** over tighten Luer connections. Tighten connections **only** until slight resistance is felt.

- a. Remove **Green** inlet cap on top of Cartridge and connect primary I.V. to connector of Cartridge marked **IN**. Remove **Blue** outlet cap on bottom of Cartridge and connect the extension set to the connector at bottom of the Cartridge marked **OUT**. Ensure there are **no** kinks in any tubing.

Anesthesia Safety Products - Confidential Information

This document and the subject matter contained hereon is the property of Anesthesia Safety Products and may not be copied, reproduced, or disclosed to others without the expressed written permission of a duly authorized agent of the company.

- b. Turn the Device on. All front panel indicators (9) will illuminate for 3 seconds, then only the **ON** button and 3 battery lights (indicating AC power is present) will remain lit. If any other Indicator lights stay on or if there is an audible alarm, refer to Operator’s Manual and follow instructions. Record information regarding all indicators / alarms on the Operative Report.
- c. Start fluid flow for the primary I.V. lines. The Cartridge will fill with fluid; any air in line will be detected and diverted into the Collection Bag. When free of air, flow will then be diverted back to extension line. Once air free I.V. fluid clears the extension line, connect to the patient.

WARNING: The AirPurge System *cannot* purge air from I.V. extension line between AirPurge System and patient. The I.V. extension line must be cleared of air before connected to patient. Failure to clear extension line could result in introduction of air to patient that could result in death or serious injury.

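### Purge frequency has no use-time denominator, and a plain mean of the time between purges leaves out the interval cut off at end of use and every subject with 0 or 1 purge

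*Combined protocol and SAP*

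**What the plan says.** The second objective in section 2.1 is to measure the "frequency and duration of the AirPurge purging mechanism activity". Section 7.0 plans the "Frequency of AirPurge purge mechanism activity (mean, range and SD) for individual study subjects" and for the whole study population, to address how necessary purging is in the course of a procedure. It gives two examples of what is meant: "e.g. number of purging episodes; length of time between purging episodes".

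Observation of a subject stops with device use (section 3.1): "The study endpoint is the discontinuation of AirPurge System usage during the procedure". Two measures of use time are collected: "AirPurge Start Time and End Time" on the Operative Report (section 6.3) and "Total Time AirPurge device powered on" from the Data Monitor (section 6.4).

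The Study Summary promises a time analysis of purging activity, and section 7.0 ends with a graph of device usage over the procedure. Neither place defines a rate, a rule for the interval between the last purge and end of use, or a rule for subjects with fewer than two purges.

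At start-up the device is switched on and clears the line before the patient is attached (section 5.9): "Once air free I.V. fluid clears the extension line, connect to the patient". The plan does not say whether purges in that phase count as episodes, or whether the recorded start time falls before or after it.

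**The concern.** The number of episodes per procedure is a valid summary, but it mixes how often the device purges with how long it was used. The eligible procedures run from balloon dilatation to spinal fusion and bypass surgery, so use time may differ widely.

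The time between episodes has another weakness. A completed gap needs two purges, so subjects with 0 or 1 purge contribute nothing. The interval running when use ends is also lost, and long intervals are the likeliest to be running then. A plain mean of what remains is therefore too short for the gaps it is meant to describe, and enrolling more subjects does not correct this. The study is descriptive with no success criteria, so these summaries are its result.

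**Working it through.** **Inputs.** The measures, end of observation and collected times are from sections 7.0, 3.1, 6.3 and 6.4. The planned total of 200 to 300 subjects is from section 3.3. The documents give no purge rate or use time, so there is no figure of the plan's own to reproduce. Assumed: μ = 2, 5, 10 or 20 expected purges per subject, and use time T either fixed or uniform on 1 to 6 h (mean 3.5, variance 25/12).

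**Step 1: episode counts.** At 2 purges per hour for everyone, the mean count is 2 for 1 h of use and 12 for 6 h. With T uniform, the share of count variance due to use time alone is r²(25/12) / [r²(25/12) + 3.5r]. At r = 2 per hour this is 8.33/(8.33 + 7) = 54%. It is 37% at 1 per hour and 70% at 4 per hour.

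**Step 2: completed gaps, fixed T, constant Poisson rate.** The share of subjects with no gap is e^(−μ)(1 + μ): 41% at μ = 2, 4% at μ = 5 and about 0 from μ = 10. Given n purges, each of the n − 1 completed gaps has expectation T/(n + 1). The true mean gap is T/μ. The ratio of pooled to true mean gap is therefore μA/B, where

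- A = E[(N−1)⁺/(N+1)] = 1 − 2(1 − e^(−μ))/μ + e^(−μ)
- B = E[(N−1)⁺] = μ − 1 + e^(−μ)

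At μ = 2: A = 1 − 0.8647 + 0.1353 = 0.2707, B = 1.1353, ratio 2 × 0.2707/1.1353 = 0.477. At μ = 5: 5 × 0.6094/4.0067 = 0.761. If each subject's gaps are averaged first, the ratio is μ·E[1/(N+1) | N ≥ 2].

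**Step 3: other assumptions.** Each entry is the mean gap divided by use time per expected purge.

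| Scenario | μ = 2 | 5 | 10 | 20 |
|---|---|---|---|---|
| Fixed T, pooled gaps | 0.477 | 0.761 | 0.889 | 0.947 |
| Fixed T, mean of subject means | 0.544 | 0.912 | 0.998 | 1.000 |
| T 1–6 h, pooled | 0.533 | 0.780 | 0.891 | 0.947 |
| T 1–6 h, mean of subject means | 0.59 | 0.87 | 0.97 | >0.99 |
| T 1–6 h, rates vary (gamma shape 4), pooled | 0.479 | 0.709 | 0.836 | 0.916 |
| Same, mean of subject means | 0.56 | 0.91 | 1.12 | 1.25 |
| T 1–6 h, regular gaps (gamma shape 4), start-up purge counted, pooled | 0.854 | 0.946 | 0.974 | 0.987 |

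Values above 1 in the sixth row do not mean that the censoring bias has reversed. With shape 4, the mean of subjects' own true gaps is 4/(4 − 1) = 1.33 times use time per purge, and 1.12 and 1.25 are still below it. That row estimates a different quantity from the overall rate.

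**Step 4: the rate.** In simulated studies of 200 subjects (T 1–6 h, common rate, μ = 5), total purges divided by total use time averaged 1.001 of the truth (SD 0.031). The pooled gap averaged 0.780 (SD 0.026). A subject-level bootstrap 95% CI for the rate covered 93% to 96% across a common rate and gamma shapes 4 and 1, at 2, 5 and 20 purges, with 200 and 300 subjects. These runs make rate independent of use time. If it is not, the pooled rate and the mean subject rate differ, so both are worth reporting.

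**Step 5: the window.** One line-clearing purge per subject, counted without its time, raises the rate by 1/μ: 50%, 20%, 10% and 5%. Counting its time as well helps little. With an assumed 5 minutes added to 3.5 h, the rate ratio at μ = 2 is (3/3.583)/(2/3.5) = 1.465, still 46.5% high. At μ = 5 it is (6/3.583)/(5/3.5) = 1.17, or 17% high.

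**The case against.** The two measures are only examples, and section 7.0 fixes no gap formula. Individual-subject summaries are planned, and on that reading the shortfall is nearly gone by 10 purges. The Study Summary and section 7.0 both plan to look at purging over time. Use time is recorded, so a rate could be computed later without loss. Bag changes may make purges more regular (section 5.11: "The AirPurge will remove air admitted into primary I.V. line and divert liquid flow back to study subject line"), which shrinks the bias. If the start-up purge counts, subjects with 0 purges should be rare. Every magnitude is assumed.

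Most of this stands, and it limits the size of the problem. A reader might infer that the plan ignores time or cannot yield a rate. The documents do not support that: the data are collected and a time analysis is intended. A reader might also infer that start-up purges will be counted against the wrong time. No passage says so; the window is simply undefined, and the Data Monitor's purge count and powered-on time may well share one.

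The objection does not supply a denominator, a rule for the last interval or a rule for subjects with fewer than two purges. Individual data and a graph would show part of the problem, but the overall mean gap would still be off. Nothing in the documents shows that purges will be numerous or regular enough to make it negligible.

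**Conclusion.** The point holds as an analysis gap that should be closed, with medium confidence. The omission follows from the definition of a completed gap; its size rests on assumptions. With a constant Poisson rate and 1 to 6 h of use, the shortfall at 2, 5, 10 and 20 purges is 47%, 22%, 11% and 5% for pooled gaps, and 41%, 13%, 3% and under 1% for the mean of subject means. With regular purging and a counted start-up purge, the pooled shortfall is 15% or less. The bias matters mainly when purges per subject are few or irregular.

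It is tempting to conclude that the mean gap will always make purging look more frequent than it was. That goes too far. If rates vary between subjects, the mean of subject means can exceed total use time divided by total purges, by about 12% at 10 purges and 25% at 20 under gamma shape 4, because it estimates a different quantity. Section 7.0 does not say which form of mean is meant, so the direction relative to the overall rate is not fixed.

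**What to change.** In section 7.0:

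1. Add purges per hour of AirPurge use: total episodes divided by total use time, with a 95% CI by subject-level bootstrap, and the mean, SD and range of subjects' own rates.
2. Keep episodes per procedure, shown alongside use time.
3. For the analysis, count both purges and use time from patient connection to end of use. Report line-clearing purges separately, and define the recorded AirPurge Start Time to match.
4. If gaps are reported, treat the last one as censored at end of use, state whether gaps are pooled or averaged by subject, and give the number of subjects with 0 and with 1 purge.

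The cost is a few sentences, slightly more analysis work and a defined start time. No new data field is needed: start and end times are already on the Operative Report, powered-on time can serve as a check, and the planned gap summary and time graph already require purge times.

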8.0 SAFETY ISSUES

8.1 AIRPURGE SYSTEM INDICATOR LIGHTS / ALARMS

Device performance in the clinical setting will be monitored as part of this post-approval study. The incidence and timing of AirPurge System Indicator Lights and Alarms during the procedure will be described on the CS001-13LL Operative Report with objective data collected via the Data Monitor. The incidence of procedure complications will also be recorded on the CS001-13LL Operative Report.

8.2 PROTOCOL DEVIATIONS, DEVICE COMPLAINTS AND REPORTABLE EVENTS

NOTE: The following safety data will be collected for Study Sponsor notification as described below. Clinical Site personnel will be responsible for notifying the Study Sponsor within 24 hours of any device complaints, potential medical device reporting (MDR) reportable events or significant protocol deviations. In addition, Clinical Sites conducting this post-approval study under Institutional Review Board (IRB) oversight will follow the guidelines outlined by their overseeing IRB for the reporting of the incidence of device complaints, medical device reporting (MDR) reportable events (including IRB notification and the completion of Form 3500A Medwatch Forms), as appropriate or significant protocol deviations.

Clinical Investigators / participating Clinical Sites should make every effort to comply with all aspects of this post-approval clinical protocol and *not* deviate in any way from the standardized protocol requirements. The Clinical Site will document any protocol deviations that may occur on the Operative Report and for Clinical Sites conducting the post-approval study under IRB oversight, the Principal Investigator will be responsible for submitting any *significant* protocol deviations to the IRB for review, based on individual IRB requirements. The Study Sponsor should be notified of any *significant* protocol deviations within 24 hours of occurrence.

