8.3 DEFINITIONS

Complaint: Any written, electronic or oral communication that alleges deficiencies related to the identity, quality, durability, reliability, safety, effectiveness, or performance of a device after it is released for distribution.

Medical Device Reporting (MDR) Reportable Event (or Reportable Event):

- (1) An event that user facilities become aware of that reasonably suggests that a device has or may have caused or contributed to a death or serious injury; or
- (2) An event that manufacturers or importers become aware of that reasonably suggests that one of their marketed devices:

Anesthesia Safety Products - Confidential Information

This document and the subject matter contained herein is the property of Anesthesia Safety Products and may not be copied, reproduced, or disclosed to others without the expressed written permission of a duly authorized agent of the company.

- (i) May have caused or contributed to a death or serious injury, or
- (ii) Has malfunctioned and that the device or a similar device marketed by the manufacturer or importer would be likely to cause or contribute to a death or serious injury if the malfunction were to recur.

Serious Injury: An injury or illness that:

- (1) Is life-threatening,
- (2) Results in permanent impairment of a body function or permanent damage to a body structure, or
- (3) Necessitates medical or surgical intervention to preclude permanent impairment of a body function or permanent damage to a body structure.

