8.4 MEDICAL MONITORING

It will be the responsibility of the Principal Investigator at each Clinical Site to closely monitor not only the overall study conduct at their Clinical Site but to oversee the safety outcomes from all study procedures. The Medical Monitor will be responsible for reviewing data from all Clinical Sites and providing guidance to the Investigator group, as necessary.

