9.3 RECORDS/MATERIALS TO BE MAINTAINED

The Principal Investigator will maintain *copies* of the completed CS001-12LL Eligibility Checklist / Demographics and CS001-13LL Operative Report CRFs, all completed / signed Informed Consent Documents (*if applicable*), all IRB correspondence (*if applicable*) and the Clinical Study Binder. The Clinical Site will send the *original* completed CS001-12LL Eligibility Checklist / Demographics and CS001-13LL Operative Report CRFs to Anesthesia Safety Products on a periodic basis throughout the duration of the post-approval study. The Clinical Site will return the Data Monitor to Anesthesia Safety Products upon completion of the *last* procedure. These records will be considered confidential and proprietary to Anesthesia Safety Products. Clinical Sites under the oversight of an IRB will follow their IRB's requirements for the length of record retention (typically a minimum of 2 years).

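### A suspected air embolism carries no 24-hour duty under 8.2 if the site sees no possible device role or the injury is not serious, unless a device complaint or significant deviation accompanies it

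*Combined protocol and SAP*

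**What the plan says.** **The 24-hour rule.** Section 8.2 makes sites responsible for "notifying the Study Sponsor within 24 hours of any device complaints, potential medical device reporting (MDR) reportable events or significant protocol deviations".

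**The definitions.** Under 8.3 a complaint is a "communication that alleges deficiencies related to the identity, quality, durability, reliability, safety, effectiveness, or performance of a device". A reportable event, on the user-facility limb, is one that "reasonably suggests that a device has or may have caused or contributed to a death or serious injury". A further limb, for manufacturers and importers, adds malfunctions likely to lead to such harm if repeated. Serious injury means a life-threatening event, permanent harm, or harm needing intervention to prevent permanent damage.

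**Procedure complications.** Section 8.1 states: "The incidence of procedure complications will also be recorded on the CS001-13LL Operative Report". Section 6.3 lists a field for them. Under 9.3 the original forms go "to Anesthesia Safety Products on a periodic basis throughout the duration of the post-approval study". No interval is given.

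**Outside review.** Section 8.4 states: "The Medical Monitor will be responsible for reviewing data from all Clinical Sites and providing guidance to the Investigator group, as necessary". Section 11.3 has the sponsor review outcomes for safety. Neither section gives a time.

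**The concern.** Air embolism is the clinical event most closely tied to this device. Lowering its risk is part of the first benefit listed in 1.5.3. Section 5.5 warns that air left in the extension line, which the device cannot purge, may kill or seriously injure the patient. Subjects may weigh as little as 5 kg (4.1). The eligible procedures include craniotomy, spinal fusion and cardiac surgery with bypass, so a surgical explanation may come readily to a site.

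Whether the air came from the line or the operative field is first judged at the site. If that judgement is wrong, or if an embolism without serious injury is an early sign of a line problem, someone who sees all sites should learn of it soon. Nothing in 8.2 requires this. What is at stake is the speed of an outside check. The estimates of air volume and purge activity are not affected.

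**Working it through.** No arithmetic applies. The documents give neither an event rate nor an interval for sending forms, so no waiting time can be computed. The check is to put cases through the three triggers.

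| Suspected air embolism during AirPurge use | Complaint | Potential MDR event | Significant deviation | 24-hour duty |
|---|---|---|---|---|
| A. Serious; site sees no possible device role; nothing else reported | No: no deficiency alleged | No: nothing suggests a device contribution | No | **None** |
| B. Device role possible; not a serious injury; no malfunction; nothing else reported | No | No: death or serious injury is required | No | **None** |
| C. Serious; device role possible | Not needed | Yes | Not needed | Yes |
| D. Malfunction likely to cause death or serious injury if it recurred | Not needed | Yes, on the manufacturer limb | Not needed | Yes |
| E. Any embolism with a device complaint | Yes | Not needed | Not needed | Yes |
| F. Any embolism with a significant deviation | Not needed | Not needed | Yes | Yes |

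Cases A and B are the gap.

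Next, follow A and B through the rest of the protocol:

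1. The event is entered as a procedure complication (8.1, 6.3). Section 9.2 has the form completed at or soon after surgery, but that governs completion, not sending.
2. The form goes to the sponsor periodically (9.3).
3. If the subject is withdrawn, the sponsor is also told, with no time limit (4.4.2).
4. Related clues travel on the same form. For alarms, 5.14 states: "The incidence and timing of any Indicator Light or Alarm will be documented on the Operative Report". For deviations, 8.2 states: "The Clinical Site will document any protocol deviations that may occur on the Operative Report".
5. The Data Monitor record is collected when a site finishes enrolling. Earlier collection is optional and is meant to check that the monitor works (6.1).
6. IRB oversight is optional (10.3). Where it exists, the reporting described in 8.2 covers the same kinds of event.
7. Sponsor and Medical Monitor review follow, without a stated time (11.3, 8.4).

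The contrast is therefore 24 hours for C to F against an unstated time for A and B. The study has 200-300 subjects and a stated duration of 6-8 weeks.

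**The case against.** The strongest reply is that the gap is narrow and the sponsor is active. The MDR trigger covers potential events, and its test is whether the device may have contributed. With the device on the active line, a careful site would report many suspected embolisms. The sponsor checks all forms and chases missing ones (11.1) and keeps in continuous contact with sites (11.2). The device is marketed and used on-label, routine air checks continue below it (1.5.1, 5.2), and the study has no safety endpoints.

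Most of this stands, and it sets the severity. It does not close the gap. The low causal threshold does not help in case B, where seriousness is missing. The contacts in 11.2 are described as covering enrolment, form completion, consent and IRB requirements, and troubleshooting; complications are not named. None of these provisions sets a safety clock.

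A reader might infer more than the documents support:

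- *The whole 24-hour rule turns on the site's attribution.* It does not. The complaint and significant-deviation triggers need no causal judgement about the event.
- *The site alone decides, or such events go unrecorded.* They are recorded, and both the sponsor and the Medical Monitor review study data. Only the timing is missing.
- *The Medical Monitor does not receive 24-hour reports.* No text forwards them, but data from all sites are within that role's remit, and routing may be set out in sponsor procedures that are not shown.
- *The Operative Report cannot hold air found below the device.* The form itself is not in the documents, only its field names. The fields for complications, complaints and other line activity could each hold it.

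**Conclusion.** The point holds, at low severity, as a cheap improvement. A suspected air embolism with neither a device complaint nor a significant deviation has no 24-hour duty when the site sees no possible device role, or when the injury is not serious and there is no qualifying malfunction. The shortfall is in the speed of an outside check, not in capture or review. Its size is unquantified.

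The conclusion rests on reading 8.2 and 8.3 as written. It assumes that no sponsor procedure outside these documents already imposes an earlier report. If one does, the fix only brings the protocol into line with it.

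**What to change.** In 8.2, add to the 24-hour list: *any suspected or confirmed air embolism during AirPurge use, regardless of attributed cause or seriousness*.

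Optionally, add one sentence to 8.4 saying that the sponsor passes these reports to the existing Medical Monitor on receipt.

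No extra Operative Report line is needed, and bubbles cleared routinely below the device stay outside the 24-hour rule.

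The cost is one phrase, plus one sentence if the option is taken, with no new committee, visits or subjects. The downside is that some 24-hour reports will prove purely surgical. Their number is expected to be small, but the documents give no rate from which to estimate it.
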